9.12. COVID-19 Related Analyses

In accordance with FDA guidance document "FDA Guidance on Conduct of Clinical Trials of Medical Products during COVID-19 Pandemic" [8], we will perform additional analyses to assess the effect of the COVID-19 pandemic on the study outcomes. Additional COVID-19 related analyses may be performed.

9.12.1. COVID-19 Timing Poolability Analysis

The primary endpoint for subjects can be classified as 1) taken before the COVID-19 impact; and 2) during the COVID-19 pandemic. On 24MAR2020 a letter was sent to all study sites to suspend enrollment. Any 6-month follow-up visits performed before this date will be classified as "before COVID-19 impact", while those on or after this date will be classified as "during COVID-19 impact". The following poolability analysis will be performed between the COVID-19 impacted groups defined above.

- A linear regression will be performed, with change in 24-hour SBP from baseline to 6 months as the dependent variable, and baseline 24-Hour SBP, treatment, COVID-19 indicator, treatment * COVID-19 interaction as independent variables. If the interaction term is not significant at 0.15 level, then the primary efficacy endpoint results are considered consistent between COVID-19 subgroups.

9.12.2. COVID-19 Randomization Date Poolability Analysis

Any subjects randomized on 1AUG2019 or later will have their 6 month efficacy endpoint visit during the COVID-19 pandemic period. The following poolability analysis will be performed between subjects randomized before vs. on or after 1NOV2019.

- A linear regression will be performed, with change in 24-hour SBP from baseline to 6 months as the dependent variable, and baseline 24-Hour SBP, treatment, COVID-19 randomization date indicator, treatment * COVID-19 randomization date indicator interaction as independent variables. If the interaction term is not significant at 0.15 level, then the primary efficacy endpoint results are considered consistent between COVID-19 subgroups.

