The safety endpoints will be adjudicated by the Clinical Events Committee (CEC). The following algorithm will be used to evaluate the safety event rates: The denominator will include all subjects who either had a CEC adjudicated event prior to the time of interest (180 days for 6 months events, for example), or had last contact date that is beyond the lower window of the follow up (166 days for 6 month events, for example). The numerator will include all subjects who had CEC adjudicated events up to the time of interest (180 days for 6 months events, for example).

The secondary safety endpoints, out to 6-months follow-up, will be compared between RDN and control groups using Fisher's exact test. Two-sided 95% confidence intervals of the difference between treatment groups will also be presented.

After 6-months follow-up, control subjects may crossover (undergo renal denervation), and secondary safety endpoints will be summarized by group (RDN, Crossovers, Non-Crossovers). RDN vs. Crossover vs. Non-Crossover groups will be compared out to 36 months post-procedure using chi-square tests for categorical data and ANOVA for continuous data.

The secondary safety analyses will be performed using the ITT population defined in section 9.1.3.1.

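### The COVID-19 randomization-date analysis (SAP 9.12.2) gives 1AUG2019 as the date from which subjects are affected but splits at 1NOV2019, and neither date matches the 24MAR2020 cut in 9.12.1

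*SAP*

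**What the plan says.** SAP section 9.12.1 dates the pandemic's impact by one operational event: "On 24MAR2020 a letter was sent to all study sites to suspend enrollment". A 6-month visit before that date counts as before the impact, and a visit on or after it counts as during the impact. The section then tests a treatment-by-COVID-19 interaction on the 6-month change in 24-hour SBP.

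Section 9.12.2 repeats that regression with randomization date in place of visit date. Its opening sentence is the rationale: "Any subjects randomized on 1AUG2019 or later will have their 6 month efficacy endpoint visit during the COVID-19 pandemic period". The next sentence sets the split: "The following poolability analysis will be performed between subjects randomized before vs. on or after 1NOV2019". The decision rule is: "If the interaction term is not significant at 0.15 level, then the primary efficacy endpoint results are considered consistent between COVID-19 subgroups". The section gives no pandemic start date of its own and no reason for moving from August to November.

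**The concern.** The only apparent purpose of the first sentence is to justify a cut date, yet the cut that follows is three months later. Taken literally, the section describes a set of subjects as pandemic-affected and then assigns them to the comparison group.

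The section also does not fit 9.12.1, the one place where the SAP puts a calendar date on the pandemic's impact. Six months after 1AUG2019 falls well before 24MAR2020, and six months after 1NOV2019 falls well after it.

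What is at stake is the meaning of a non-significant result. The rule reads non-significance at the 0.15 level as consistency. If the treatment effect does differ in the pandemic period, pandemic-period subjects in the earlier group pull the two groups together and make that reading more likely. Conflicting dates also leave the programmer to choose one, and a choice made after unblinding would be post hoc.

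**Working it through.** **Inputs**
- Rationale date 1AUG2019 and split date 1NOV2019 (SAP 9.12.2).
- Visit cut 24MAR2020 (SAP 9.12.1).
- Six months taken as 180 days, with a lower window edge of 166 days. Both are examples given for safety event rates in SAP 9.9.2: "had a CEC adjudicated event prior to the time of interest (180 days for 6 months events, for example" and "had last contact date that is beyond the lower window of the follow up (166 days for 6 month events, for example".
- Upper window edge of 194 days. This is an assumption, symmetric about day 180 (180 + 14), and is not stated in the SAP.
- Visits counted from the randomization date, as 9.12.2 itself does.

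**Step 1. Forward: randomization date + interval = visit date**

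| Randomized | +166 d | +180 d | +6 calendar months | +194 d | Days to 24MAR2020 |
|---|---|---|---|---|---|
| 1AUG2019 | 14JAN2020 | 28JAN2020 | 1FEB2020 | 11FEB2020 | 236 |
| 31OCT2019 | 14APR2020 | 28APR2020 | 30APR2020 | 12MAY2020 | 145 |
| 1NOV2019 | 15APR2020 | 29APR2020 | 1MAY2020 | 13MAY2020 | 144 |

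At 180 days, the 1AUG2019 subject is seen 236 − 180 = 56 days before the cut, and the 1NOV2019 subject 180 − 144 = 36 days after it. A subject randomized on 31OCT2019 would need a visit by day 144 to count as before 24MAR2020, which is earlier than the 166-day lower edge.

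**Step 2. Backward: 24MAR2020 − interval = matching randomization date**

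| Interval | Matching date | Days from that date through 31OCT2019 | Days from 1AUG2019 up to that date |
|---|---|---|---|
| 166 d | 10OCT2019 | 22 | 70 |
| 180 d | 26SEP2019 | 36 | 56 |
| 6 calendar months | 24SEP2019 | 38 | 54 |
| 194 d (assumed) | 12SEP2019 | 50 | 42 |

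Neither 1AUG2019 nor 1NOV2019 is reproduced under any of the four intervals.

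**Step 3. Who is in the earlier group under a 1NOV2019 split**
- By the first sentence of 9.12.2: every subject randomized 1AUG to 31OCT2019, which is 31 + 30 + 31 = 92 days of randomization, is a pandemic-period subject in the earlier group.
- By the 24MAR2020 rule: subjects randomized from about 24–26SEP to 31OCT2019, which is 36 to 38 days nominally, with a range of 22 to 50 days.
- The later group is clean under the 24MAR2020 rule if visits are in window, since its earliest in-window visit is 15APR2020.

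The 24MAR2020 rule also contradicts the 1AUG2019 sentence. Subjects randomized from 1AUG2019 to about 23–25SEP2019 (54 to 56 days) would have nominal visits before the cut.

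**Step 4. Direction of the effect on the test**
Let the treatment effect differ by δ between pandemic and pre-pandemic subjects. Let a fraction f of the earlier group be pandemic-period subjects, the same in both arms, and let the later group be entirely pandemic-period. The expected interaction contrast is then δ − fδ = (1 − f)δ, so it shrinks toward zero as f rises. The SAP gives no enrollment by date, so f and the loss of power at the 0.15 level cannot be computed.

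**The case against.** The strongest reply is that the question is tested properly elsewhere. Section 9.12.1 classifies each subject by the actual date of the 6-month visit and fits the same interaction model at the same level, so a subject randomized in October 2019 and seen in April 2020 is classed correctly there. This stands. A reader might infer from 9.12.2 that the plan's whole COVID-19 assessment is tilted toward consistency; the documents do not support that.

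Second, 24MAR2020 is the date of a letter suspending enrollment, and 9.12.2 speaks of a pandemic period without saying when it began. An earlier start, around 1FEB2020, would fit the 1AUG2019 sentence. That is possible, and it makes the conflict with 9.12.1 less direct than the conflict inside 9.12.2. It does not rescue the split, because an earlier start puts more pandemic-period subjects in the earlier group.

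Third, 24SEP2019 appears nowhere in the SAP, and a split there would make 9.12.2 close to a repeat of 9.12.1 with a less accurate proxy. This also stands as a caution: a reader might infer that 24SEP2019 was the intended date, but the SAP does not show which date was meant.

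Fourth, the harm is counted in calendar days, not subjects. That is correct. Few or many subjects may have been randomized in those weeks, so only the direction of any dilution can be stated, and only if an interaction exists.

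A deliberate later cut is conceivable, but then the rationale sentence is wrong and the real reason is absent, so the text needs correcting either way.

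**Conclusion.** The point holds. Section 9.12.2 contradicts itself, and neither of its dates maps to the 24MAR2020 rule. Under either definition of the pandemic period, a 1NOV2019 split leaves pandemic-period subjects in the earlier group. The 22-day end of the range under the 24MAR2020 rule rests on applying the 166-day lower edge, given for safety events, to the efficacy visit; the 50-day end rests on the assumed upper edge. The existence of the mismatch depends on neither.

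Severity is minor. This is one of several supportive COVID-19 checks, and 9.12.2 attaches no action to a significant interaction. The split does not enter the primary Bayesian analysis (9.9.4) or the stopping rules (9.8). A reader might infer that a study conclusion is at risk or that a bias of known size has been shown; the SAP supports neither.

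**What to change.** Before unblinding, use one randomization cut date in both sentences of 9.12.2 and for the indicator variable, and state the reason for it. There are two ways to do this:

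- Keep the 9.12.1 definition of impact and use the matching randomization date, about 24SEP2019 (24MAR2020 minus six calendar months).
- If a different pandemic start is intended, state that start in 9.12.2, explain why it differs from 9.12.1, and use the matching date. On the section's own first sentence that date is 1AUG2019.

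The cost is a few words of SAP text and one indicator variable. No new data are needed, and no other analysis changes.

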9.12.3. COVID-19 Positive vs. Negative Subgroup Analysis

We will identify which subjects test positive for COVID-19 and we will perform the following analysis comparing these subjects to those who do not test positive.

- A linear regression will be conducted, with 6-month change in 24-hour SBP as the dependent variable, and baseline 24-hour SBP, treatment, COVID-19 Yes/No, treatment * COVID-19 Yes/No interaction term as independent variables. If the interaction term is not significant at 0.15 level, then the treatment effect in the primary safety endpoint is considered consistent between subjects with and without COVID-19.

9.12.4. COVID-19 Method of Data Collection

An analysis will be performed to compare methods of data collection at 6-months; office visit, home visit, or remote follow-up visit (phone or virtual).

- A linear regression will be conducted, with 6-month change in 24-hour SBP as the dependent variable, and baseline 24-hour SBP, treatment, collection method (office/home/remote), treatment * collection method interaction term as independent variables. If the interaction term is not significant at 0.15 level, then the treatment effect in the primary safety endpoint is considered consistent between data collection methods.

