The prior data consists of the first consecutively randomized 80 subjects in the SPYRAL HTN-ON MED study, which were randomized in a 1:1 ratio to RDN or control. The results from these 80 subjects have already been analyzed and published [6].

The prospective data consists of the following two cohorts:

[figure not shown]
1. Subjects 81 to 106 which have already been enrolled and were randomized in a 1:1 ratio to RDN vs. control, and whose data has not been unblinded and analyzed by Medtronic.
2. All remaining subjects in the SPYRAL HTN-ON MED Study from 107 onwards which will be randomized in a 2:1 ratio to RDN vs control.

The weight of the prior data will be adjusted using a discount function, which scales from 0 to 1, according to the similarity of the prior and prospective data. The discount function adjusts the amount of weight the prior receives. This prevents the use of an informative prior where exchangeability issues are present (e.g., the prior and prospective data are quite different). This discount function approach was proposed by the Medical Device Innovative Consortium (MDIC) working group and is a collaborative

effort between FDA and industry through the MDIC [1,2]. If the analyses show a high level of agreement for prospective data compared to the prior, the prior will be weighted at or near 100%. If the prospective data perform much worse than or much better than the prior, then the prior will receive very little or zero weight. The Bayesian adaptive design is set up to enroll patients until a sufficient sample size is achieved to have high probability of meeting the endpoint.

The sample size of the study will vary from a minimum of 110 to 221 subjects with evaluable data due to the adaptive nature of the trial. This will require approximately 130 to 260 randomized subjects assuming a 15% rate of attrition at 6-months.

- The first interim analysis will take place when we have a minimum of 110 subjects with evaluable data. With an expected attrition rate of 15%, this will require approximately 130 randomized subjects. If the attrition rate is higher than 15%, then additional subjects will be randomized in order to reach a minimum of 110 evaluable subjects.

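### The treatment-by-collection-method test in section 9.12.4 is not separated from a treatment-by-period difference; fit it within the pandemic period or add the 9.12.1 period terms

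*SAP*

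**What the plan says.** Section 9.12 introduces the COVID-19 work as supplementary: "we will perform additional analyses to assess the effect of the COVID-19 pandemic on the study outcomes". Two of its parts matter here.

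- **Section 9.12.1 (period).** "The primary endpoint for subjects can be classified as 1) taken before the COVID-19 impact; and 2) during the COVID-19 pandemic". The cut is the date of the 6-month visit relative to 24MAR2020. The regression uses "baseline 24-Hour SBP, treatment, COVID-19 indicator, treatment * COVID-19 interaction as independent variables", and the interaction is judged at 0.15.
- **Section 9.12.4 (method).** "An analysis will be performed to compare methods of data collection at 6-months; office visit, home visit, or remote follow-up visit (phone or virtual"). The regression of 6-month change in 24-hour SBP uses "baseline 24-hour SBP, treatment, collection method (office/home/remote), treatment * collection method interaction term as independent variables". The only decision rule is on the interaction: "If the interaction term is not significant at 0.15 level, then the treatment effect in the primary safety endpoint is considered consistent between data collection".

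The period model contains no method term. The method model contains no period term and is not limited to any calendar window. The method main effect has no stated test or conclusion. The rule names the safety endpoint although the outcome modelled is blood pressure; I read it as meaning the blood-pressure treatment effect.

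**The concern.** Home and remote 6-month visits are listed as part of the pandemic response, so it is reasonable to expect almost all of them after the cut. Office visits presumably took place both before and after it. The office level would then be a mixture of eras, while the other two levels belong to one era.

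Comparing the treatment effect between office and home or remote visits would therefore also compare, in part, the earlier era with the later one. The plan tests treatment-by-period in 9.12.1, so it regards an effect that varies by era as worth checking, but it omits that term from the method model.

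At stake is the attribution of a result. A significant interaction could come from era rather than method. A non-significant one, which the plan would read as consistency, could be a real method difference offset by an opposite era difference.

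**Working it through.** Section 9.12.4 states no sample size, power or effect size, so there is no planned figure to reproduce. The check has two parts.

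**1. Size of the spurious difference**

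Let s be the share of office visits before 24MAR2020, E_pre and E_dur the treatment effects in the two eras, and d the size of their difference. Assume no true method effect and no home or remote visits before the cut.

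- Office effect = s × E_pre + (1 − s) × E_dur
- Home or remote effect = E_dur
- Difference = s × (E_pre − E_dur), which has size s × d

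The SAP gives neither s nor d, and 9.12.4 does not say whether the first 80 subjects are included, which also affects s. I take s = 40–80% as an assumed range.

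| d (mmHg) | s = 40% | s = 80% |
|---|---|---|
| 2.05 | 0.8 | 1.6 |
| 3 | 1.2 | 2.4 |
| 5 | 2.0 | 4.0 |

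The first row uses the only between-cohort difference in the SAP (section 9.9.4.3, Table 3). The prior effect is −8.85 − (−1.80) = −7.05 mmHg and the expected prospective effect is −5.0 mmHg, a gap of 2.05. Those cohorts do not coincide with the COVID-19 eras, so this gives only a scale. The last row sets d equal to the whole planned effect and is an extreme case.

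**2. Effect on the decision at 0.15**

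The 9.12.4 regression was simulated with no true method effect, 3,000 trials per scenario.

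- *From the SAP:* SD 12 mmHg, treatment effect −5.0 mmHg and 15% attrition (Table 3); 1:1 allocation to subject 106, then 2:1 (section 8).
- *Assumed:* 260 subjects, 140 with the 6-month visit before the cut and 120 after; home and remote visits only after the cut, at 20%, 40% or 60% of those visits; baseline slope −0.3.

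These counts imply s = 140/(140 + 96) = 59%, 140/(140 + 72) = 66% and 140/(140 + 48) = 74%.

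Proportion of trials in which the planned treatment-by-method test is significant (nominal 15%):

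| Scenario | 20% home/remote | 40% | 60% |
|---|---|---|---|
| No era difference | 16% | 14% | 15% |
| Calendar shift of 5 mmHg in both arms | 15% | 14% | 16% |
| Treatment effect differs by 5 mmHg between eras | 18% | 23% | 27% |
| Both | 14% | 16% | 22% |

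Monte Carlo standard error is √(0.15 × 0.85 / 3000) ≈ 0.7 percentage points.

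Under the plain shift, the method main effect was significant in 29%, 45% and 62% of trials, but the plan draws no conclusion from that term.

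The change in allocation lets a plain shift leak slightly into the office treatment effect. In the 40% case:

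- Before the cut: 53 + 22.7 = 75.7 RDN and 53 + 11.3 = 64.3 control visits.
- Office visits after the cut: 48 RDN and 24 control.
- Post-cut share of office visits: 48/123.7 = 38.8% for RDN and 24/88.3 = 27.2% for control.
- Leak from a 5 mmHg shift: 5 × (0.388 − 0.272) ≈ 0.6 mmHg.

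This is too small to move the test visibly. It is also why s × d is approximate. With both differences present, the leak works against the spurious interaction, which is consistent with the lower rates in the last row.

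With period and treatment-by-period added, or with the data restricted to visits after the cut, the interaction test was significant in 13–16% of trials in every scenario.

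**The case against.** A reader might infer that any calendar difference in blood pressure would be reported as a method difference. The SAP does not support that. Its only rule rests on the interaction, and a shift common to both arms leaves that test at its nominal rate. Only a treatment effect that itself differs by era carries over, and only the fraction s of it.

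The best defence is that 9.12.1 already tests treatment-by-period on the same outcome, at the same level, and its result will be read alongside 9.12.4. That helps interpretation but does not separate the two explanations. One model has period without method and the other has method without period, so a signal in either could belong to the other. A non-significant 9.12.1 result does not show that d is zero.

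Three further objections stand:

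- The SAP does not say that home and remote visits were confined to the pandemic.
- It gives no visit counts, so s and d are assumptions throughout.
- The analysis is supplementary, and 9.12.4 attaches no action to a significant result.

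These limit the severity. They do not remove the reason for a nearly free correction.

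**Conclusion.** The point holds as a low-severity improvement. As written, the treatment-by-method test cannot be distinguished from a treatment-by-era difference. On the assumed ranges, the spurious difference is 1.2–4.0 mmHg for d of 3–5 mmHg, or 0.8–1.6 mmHg at d = 2.05. Even at d = 5 mmHg, the false-signal rate rises only from 15% to 18–27%, and to 14–22% if a calendar shift is also present. All of this rests on home and remote visits being essentially confined to the pandemic.

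It would be too strong to say that the analysis cannot address collection method at all. If office visits continued after the cut, the confounding is partial, and a within-era comparison can be made. Nothing here affects the primary Bayesian analysis, the stopping rules or the study success rule.

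**What to change.** Amend section 9.12.4 in one of two ways.

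1. Fit the model only to 6-month visits on or after 24MAR2020, the later group of section 9.12.1.
2. Keep all visits and add the 9.12.1 period indicator and its interaction with treatment.

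If home and remote visits are all after the cut, both options rest on the same comparison of methods within the pandemic period. The second also uses the earlier visits for the baseline slope and residual variance. The section should add that if few or no office visits fall after the cut, method and period cannot be separated and results will be described by method only.

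The cost is one sentence and a variable already derived for 9.12.1. Fewer office visits inform the comparison, so precision falls somewhat. The same edit should make the endpoint named in the decision rule match the blood-pressure outcome of the model.

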9.12.5. Protocol Deviation and Adverse Event Reporting

In addition to the analyses described above, we will also provide COVID-19 related protocol deviation tables and AE/SAE tables summarizing the site-reported adverse events attributed to COVID-19 as recommended by FDA guidance document.

12.1. Appendix I: Imputation of Missing Dates

Imputation of Missing AE Onset Date

Valid Portion	Missing Portion	Imputed Value for Missing Portion
Month, Year	Day	Set Day = first day of that month and year, then set the day = later of (New onset date, informed consent date).
Year	Day, Month	Set date = later of (January 1st of that year, informed consent date).
None	Day, Month, Year	Informed consent date.

Imputation of Missing Medication Start Date

Valid Portion	Missing Portion	Imputed Value for missing Portion
Month, Year	Day	Set Day = first day of that month and year
Year	Day, Month	Set date = January 1st of that year
None	Day, Month, Year	SV2 date

Imputation of Missing Medication Stop Date

Valid Portion	Missing Portion	Imputed Value for missing Portion
Month, Year	Day	Set Day = first day of that month and year, then set the day = later of (New date, SV2 date, start date).
Year	Day, Month	Set date = later of (January 1st of that year, SV2 date, start date).

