9.9.1. Primary Safety Endpoint

The primary safety endpoint of the study is the incidence of Major Adverse Events (MAE), defined as a composite of the following events through one month post-randomization (6 months for new renal artery stenosis):

- All-cause mortality
- End-stage renal disease (ESRD)
- Significant embolic event resulting in end-organ damage
- Renal artery perforation requiring intervention

- Renal artery dissection requiring intervention
- Vascular complications
- Hospitalization for hypertensive crisis not related to confirmed non-adherence with medications or the protocol
- New renal artery stenosis >70%

The primary safety analysis will be performed using the ITT population defined in 9.1.3.1.

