9.9.2. Secondary Safety Objectives

The following secondary safety endpoints will be assessed:

- Acute/Procedural Safety Secondary Endpoints – Compared Between Groups at 1 Month Post-Procedure
 - Significant embolic event resulting in end-organ damage
 - Renal artery perforation requiring intervention
 - Renal artery dissection requiring intervention
 - Vascular complications
 - End-stage renal disease (ESRD)
 - $\geq 40\%$ decline in eGFR
 - Increase in serum creatinine $>50\%$ from screening visit 2
 - New myocardial infarction
 - New stroke
 - Renal artery re-intervention
 - Major bleeding according to TIMI definition (i.e. intracranial hemorrhage, $\geq 5\text{g/dl}$ decrease in hemoglobin concentration, a $\geq 15\%$ absolute decrease in hematocrit, or death due to bleeding within 7 days of the procedure)
 - New renal artery stenosis $>70\%$
 - Hospitalization for hypertensive crisis not related to confirmed non-adherence with medication and/or protocol
- Chronic Safety Secondary Endpoints - Compared Between Groups at 3, 6, 12, 24, and 36 months post-randomization.
 - Composite Safety Endpoint, defined as a composite of the following events:
 - All-cause mortality
 - End-stage renal disease (ESRD)
 - Significant embolic event resulting in end-organ damage
 - Renal artery perforation requiring intervention
 - Renal artery dissection requiring intervention
 - Vascular complications
 - Hospitalization for hypertensive crisis not related to confirmed non-adherence with medications and/or the protocol
 - New renal artery stenosis $>70\%$

- $\geq 40\%$ decline in eGFR
- Increase in serum creatinine $>50\%$ from screening visit 2
- New myocardial infarction
- New stroke
- Renal artery re-intervention
- Major bleeding according to TIMI definition (i.e. intracranial hemorrhage, $\geq 5\text{g/dl}$ decrease in hemoglobin concentration, a $\geq 15\%$ absolute decrease in hematocrit, or death due to bleeding within 7 days of the procedure)
- Hospitalization for hypertensive crisis not related to confirmed non-adherence with medication and/or protocol
- Summary of Health-related Quality of Life (HRQoL) analysis based on reporting measures using accepted QoL instruments (EQ5D)

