9.10. Safety Evaluation

Adverse Event (AE) information will be collected by the site from subject enrollment (consent) through study termination. AEs will be followed until the event has resolved (in the case of permanent impairment, the event will be followed until it stabilizes, and the overall clinical outcome has been ascertained).

The Investigator will report any adverse events that may occur to the Sponsor, and will assess seriousness, relationship (to the device, procedure and renal denervation therapy where applicable), subsequent intervention required, resolution status and whether or not the adverse event resulted in the subject's discontinuation from the study. The Investigator will provide further information regarding adverse events as requested by the Sponsor.

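### Incomplete adverse-event onset dates are set as early as possible with consent as the only floor, so events after the procedure or the crossover can be dated before it

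*SAP*

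**What the plan says.** Appendix I of the SAP (12.1) has three rules for an incomplete adverse-event onset:

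- Day missing: "Set Day = first day of that month and year, then set the day = later of (New onset date, informed consent date".
- Day and month missing: "Set date = later of (January 1st of that year, informed consent date".
- Nothing known: the informed consent date.

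The randomization, procedure and crossover dates appear in none of them. Consent is where collection starts, according to section 9.10: "Adverse Event (AE) information will be collected by the site from subject enrollment (consent) through study termination".

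The endpoints start later. Section 9.9.1 defines the primary safety endpoint as a "composite of the following events through one month post-randomization (6 months for new renal artery stenosis". Section 9.9.2 labels the acute endpoints "Acute/Procedural Safety Secondary Endpoints – Compared Between Groups at 1 Month Post-Procedure".

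The only counting rule in the SAP is also in section 9.9.2. It says "The safety endpoints will be adjudicated by the Clinical Events Committee (CEC" and then "The numerator will include all subjects who had CEC adjudicated events up to the time of interest". It gives an upper limit (180 days for 6-month events) and a denominator, but no starting point.

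Section 9.1.4 lets control subjects cross over to denervation after their 6-month visit. Table 2 in section 9.9.1.1 lists crossovers among the sources of the 253 primary safety subjects.

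**The concern.** Consent precedes the procedure, so a consent floor lets an event that followed the procedure receive a date before it. If the analysis program starts the 1-month or 6-month window at randomization or procedure, as the endpoint labels imply, such an event is not counted.

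For crossovers the gap is longer. An event after the crossover denervation can be dated before that denervation. It then leaves the crossover contribution to the primary safety sample, and it may be counted as a control event in the 6-month comparison of denervation with control. The primary safety test is decided by a single count, so few misdated events would be needed to matter.

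**Working it through.** **1. The plan's own safety figure.** Inputs from SAP section 9.9.1.1: N = 253, performance goal 7.1%, one-sided 0.05, at most 11 subjects with an event. The exact upper bound is the 95th percentile of Beta(c + 1, 253 − c).

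- c = 11: 11/253 = 4.35%, upper bound 7.094%. This reproduces the stated 4.3% and 7.09%. P(X ≤ 11 | 253, 0.071) = 0.0496; power at a true rate of 3.5% is 82.0% (stated as 80%).
- c = 12: 12/253 = 4.74%, upper bound 7.57%, which fails.
- If one true event were always lost, 12 true events would pass, and the type I error would be P(X ≤ 12 | 253, 0.071) = 0.085.

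**2. The rules on one hypothetical subject.** Consent 3 March, procedure 20 March, event after the procedure.

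- Onset recorded as March: later of 1 March and 3 March = 3 March.
- Onset recorded as the year only: later of 1 January and 3 March = 3 March.
- Nothing recorded: 3 March.

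All three precede the procedure. The rule can also work the other way. A true onset of 25 April (day 36) recorded as April becomes 1 April (day 12), which moves the event into the 1-month window.

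**3. The rules over a year of procedure dates.** Assumptions not in the SAP: 365 equally likely procedure dates; delay to onset uniform within each range; consent 14, 30 or 60 days before the procedure (the three give the same results).

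| True onset after procedure | Known part | Dated before procedure | Dated day 0–30 | Dated after day 30 |
|---|---|---|---|---|
| Day 0–30 | month and year | 47.5% | 52.5% | 0% |
| Day 0–30 | year | 95.6% | 4.4% | 0% |
| Day 0–30 | nothing | 100% | 0% | 0% |
| Day 31–180 | month and year | 0% | 9.8% | 90.2% |
| Day 31–180 | year | 70.8% | 8.5% | 20.7% |
| Day 31–180 | nothing | 100% | 0% | 0% |

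For events on the procedure day itself, the shares dated before the procedure are 96.7% (day missing), 99.7% (year only) and 100% (undated).

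**4. Crossovers.** Onset 0–30 days after the crossover, consent date taken as the original consent, crossover assumed 210, 365 or 730 days after randomization.

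| Known part | Before randomization | Between randomization and crossover | After crossover |
|---|---|---|---|
| month and year (all three timings) | 0% | 47.5% | 52.5% |
| year, crossover day 210 | 38.1% | 57.5% | 4.4% |
| year, crossover day 365 or 730 | 0% | 95.6% | 4.4% |
| nothing | 100% | 0% | 0% |

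Not every misplaced event reaches the control arm's 6-month comparison, whose limit is day 180. With crossover at day 730, a year-only date moves back by less than a year and so lands after about day 365 (730 − 365). A fully undated event goes to consent. With no lower bound, section 9.9.2 read literally counts that as a control event; with a bound at randomization, it is counted nowhere.

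**The case against.** The strongest reply is that section 9.9.2 counts adjudicated events up to the time of interest and sets no lower bound. Read literally, an event backdated to consent in a subject randomized to denervation is still counted at 1 and 6 months. That stands. A reader might infer that Appendix I removes post-procedure events from the endpoints; the SAP does not say so, and it happens only if a lower bound is programmed. For crossovers the reply fails. The primary safety rate is defined for patients undergoing denervation, so a crossover subject can sensibly be counted only from the crossover procedure; otherwise events from the control period would be charged to denervation.

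A reader might also infer that the rule always favours the device. It does not: the second table row for day 31–180 in the working, and the one above it, show 8.5% and 9.8% of later events moving into the 1-month window. Nor do fully undated crossover events fall in the sham period; they go to consent, before randomization.

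Further points carry weight. The components of the primary endpoint are mostly tied to a procedure, an admission or imaging, and they are adjudicated, so incomplete dates are probably few. The SAP does not say, however, that the committee fixes onset dates or that Appendix I spares adjudicated events. It is also silent on whether crossovers consent again; the working assumes the original consent date.

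Finally, moving every ambiguous crossover event to after the crossover would take true control-period events out of the randomized comparison. The remedy has to avoid that.

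**Conclusion.** The point holds as a defect in a stated rule. Followed exactly, Appendix I can date a post-procedure event before the procedure and a post-crossover event before the denervation it followed. For subjects randomized to denervation, the consequence depends on a lower bound that the SAP leaves open. For crossovers, the event leaves the primary safety contribution and may be booked to control.

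The percentages rest on the assumed uniform delays and the assumed crossover times. They describe events with incomplete dates, not all events. The SAP gives no frequency of incomplete dates, so no effect on the result has been shown. The one-event margin shows how sensitive the test is, not that an event will be lost. The change should be made because it is cheap and the rule feeds a primary endpoint.

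**What to change.** In Appendix I:

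- When the known part of the date allows onset on or after the procedure, and no end date or other record (such as the visit at which the event was first reported) contradicts this, set onset to the later of the first day of the known period and the procedure date. Use the procedure date if nothing is known.
- For crossovers, use the visit of first report and any end date to place the event before or after the crossover. If it stays ambiguous, count it as post-crossover in the primary safety analysis, keep it in the control period for the 6-month comparison of denervation with control, and report a sensitivity analysis with the opposite assignment.

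In section 9.9.2, state where the counting window starts: randomization or procedure, and the crossover procedure for crossovers.

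By construction, no post-procedure event in an originally randomized subject would then be imputed to before the procedure unless another record points there. The cost is a few lines of text, the matching change to the derivation program and one sensitivity table. A few pre-procedure events may be counted as post-procedure, which would make the denervation rates slightly less favourable.
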